Tailored Messages	Created to be tailored to participants' responses on baseline questionnaire.	Someone who eats breakfast daily might receive the message: "You eat breakfast every day. That's really smart. It means you're less likely to overeat later, especially at lunch. Keep up this great habit!"

foods, etc). The lists will be used to offer recommendations based on users' location and preferences (e.g., in McDonald's a student who said they like dairy foods on the baseline survey, might be asked to try a parfait). Following completion of Aims 1 and 2 the LIITA³H system (Figure 3) will be ready for pilot testing.

[figure not shown]
C.3. Pilot Trial (Aim 3)

We will study the feasibility, acceptability and use of the LIITA³H system via a pilot with four 1-week phases. [This amendment will test the app impact on frequency of visits to, and calories purchased from, FFR in a 6-month pilot].

We have shortened our study period time frame from 6 months to 1 month due to the COVID-19 pandemic.

C.3.a. Population and Recruitment. We will recruit 150 13-17 year olds, with a BMI>85th percentile who eat at FFR at least 3 times/week) from each of the 3 cities. Recruitment and consent/assent are as above. Students will receive two \$30 gift cards as an incentive for participation. A cell phone will be provided for those who do not own one. Payment will also be provided to cover the costs of internet access for those who need it.

Due to the COVID-19 situation that hampers physical contact, recruitment for the research study trial (to replace the in-person enrollment sessions due to the COVID situation) will be conducted virtually through UMHealthResearch.org and through a Facebook and Instagram advertising campaign managed by MICHRA and linked to our UMHealthResearch study page.

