C.3.b. Enrollment Session. Upon obtaining consent /assent, an enrollment session will be scheduled. At this session students' height and weight will be measured and they will complete an online enrollment survey addressing preferences, baseline characteristics, current habits, values, ethnic identity , their level of interest in making dietary changes and any changes they might wish to make. They will download the app and receive instruction in its use, including photo submission and rating foods on a Likert scale of very healthy to very unhealthy. They will be informed that they will be randomly assigned to use one of three versions of the app by the technology team who will apply to appropriate functionality to their app.

Ame00110293

Due to recruitment and enrollment efforts being conducted virtually because of the COVID-19 pandemic, participants will be guided as they take their own height and weight measurements. Since this will be done remotely, we will send any participants who require a scale, a tape measure, a square, and/or pencils, the necessary materials, which they will be able to keep.

Randomization – The technology team will randomly assign participants as they enroll to either the intervention or one of the control groups. They will then adjust the functionality of the app for the participants accordingly, and will send a message to their phone indicating their group assignment, along with instructions for their group. Thus, the research assistant who collects data will be blinded regarding group assignment.

C.3.c. Four Week Intervention

Week 1 – Student Registration of Eating Venues. Students will be asked to identify, using ActiPal, when they are in an eating venue (cafeteria, restaurant, or convenience store). The venue data (time and location) are registered

in PiLR. They will be encouraged to submit a photo of their food choices and annotate it with a rating on the very healthy to very unhealthy scale.²⁸ By the end of week 1 the system will have collected data about the most frequent eating locations, when they typically eat there, and what food they choose.

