Week 2 – Eating Venue Identification. We will use the system to identify and contact students when they are in eating venues. We will ask students via an EMA survey whether the system is correct. For erroneous detections the appropriate stored venue criteria (location, geofence, time of day or dwell time) will be adjusted to improve detection.³⁵ For correct detections they will be asked to report on their food choice.

Throughout the study students will be able to identify newly encountered eating venues. If the app does not recognize it, they will be asked to register that location (as they did in week 1). The first assessment of eating venue recognition accuracy will be calculated. Investigators will make an overall assessment of recognition criteria and potentially correlated factors such as neighborhood or which school the student attends.

Week 3 – Delivery of Location Linked Tailored Messages. In week 3 the system will try to deliver a relevant message when a student enters an eating venue with the intent to eat. EMA surveys will elicit whether messages are appropriate (i.e., received prior to making a choice, the venue is correct, the suggested food is available), relevant (i.e., suggestion matched their preferences), and if/how it influenced their choice. At the end of week 3 the feasibility and acceptability of location linked tailored texts will be demonstrated.

Week 4 – Inclusion of EMA Questions Including Feedback. During week 4 we will assess the feasibility and acceptability of including content that provides feedback on earlier choices. The EMA tool will be used to provide information from a recent choice and to request current information (e.g., students may be reminded of the health rating of their choice from the day before and asked whether there are healthier options available today). In addition, the EMA tool will be used to congratulate students for making healthier choices and for submitting the requested photos. Students will be asked to provide their perspectives as in week 3.

For this amendment weeks 1 to 3 will not be repeated. Participants will use the app for 6 months in one of 3 groups.

We have shortened our study period time frame from 6 months to 1 month due to the COVID-19 pandemic.

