Based on students' responses when using the system we will determine 1) the percentage of the time that the system accurately identified presence in an eating venue and correctly identified the registered venue (cafeteria vs. convenience store), and 2) the percentage of time that an appropriate and relevant message was delivered.

For this amendment, calories purchased will be assessed using submitted annotated photos, and nutrition data from FFR menus (e.g., if the participant submits a picture of McDonald's fries and indicates it is a small order, then from the McDonalds menu, we will determine that the calories purchased were 240 kcals). Frequency of visits will be obtained directly from the app. We will use population averaged generalized estimating equation regressions (GEE) to compare trajectories of calories purchased and number of visits between groups. The GEE approach allows us to account for the correlation in repeated observations collected from each subject over time. For calories purchased, we will perform GEE linear regression modeling as a function of time, treatment group (intervention vs. control group 2) and the interaction of time by treatment group ($Y = \beta_0 + \beta_1 Time + \beta_2 Treatment + \beta_3 Time * Treatment + \epsilon$). Similarly, for the number of visits, we will fit a GEE Poisson regression model as a function of time, treatment group (intervention vs. control group 2 vs control group 3) and the interaction of time by treatment group. Residual diagnostics will be performed to examine departures from model assumptions. If necessary, we will use transformed outcome variables and refit the models.

Secondary Outcome 1 – Acceptability of the intervention and the messages

From the post-pilot interviews we will identify students' perceptions of the intervention overall and of the messages specifically. We will explore opinions of school personnel on impacts of using the LiTAH at school. Data from post-pilot interviews plus the advisory board input, will inform revisions of the app and planning for a larger trial.

For this amendment, we will use the models discussed above to examine associations between calories purchased /number of visits including as covariates participant characteristics such as extent of app use, initial BMI, and ethnic identity (as an ordinal measure assessed via the Multiethnic Identity Scale) as a secondary outcome.

Secondary Outcome 2 – Exploration of food choices

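### No blocking or stratification is stated and the main GEE models carry no baseline covariates; the avoidable cost is modest precision in the comparison of levels, not in the time-by-group term

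*Combined protocol and SAP*

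**What the plan says.** **Allocation.** Section C.3.b (Randomization) reads "The technology team will randomly assign participants as they enroll to either the intervention or one of the control groups". The same section tells participants that "they will be randomly assigned to use one of three versions of the app". No ratio, block size, stratification factor or pre-generated list is given.

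**Recruitment.** Section C.3.a says "We will recruit 150 13-17 year olds" and ends that sentence with "from each of the 3 cities". This can mean 150 in all or 150 per city, which is 450. A later paragraph says that recruitment "will be conducted virtually through UMHealthResearch.org and through a Facebook and Instagram advertising campaign". It does not say whether city targets still apply.

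**Main models (C.3.e).** Calories purchased are analysed by linear GEE "modeling as a function of time, treatment group (intervention vs. control group 2) and the interaction of time by treatment group". Visits are analysed by Poisson GEE with "treatment group (intervention vs. control group 2 vs control group 3) and the interaction of time by treatment group". City, sex and age are in neither. The stated purpose is to compare trajectories between groups.

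**Other uses of covariates.** A secondary analysis adds participant characteristics, with extent of app use, initial BMI and ethnic identity as examples. Sex is named only in the exploratory food-choice analysis. Under Week 2 of C.3.c, investigators are to review recognition criteria and "potentially correlated factors such as neighborhood or which school the student attends"; this concerns venue-recognition accuracy.

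**The concern.** If the sample is assembled by city, city is a natural factor to balance and adjust for. Cities may differ in how many fast food restaurants they have and how well the app detects them, and the visit count comes directly from the app. Calories purchased may differ by sex and age. If such differences exist and are neither balanced at allocation nor included in the models, they stay in the residual between-person variation.

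What is at stake depends on which model term carries the answer. Aim 3 asks whether app use goes with fewer calories and fewer visits, which is a question about levels. Under the amendment, the run-in weeks are not repeated and prompts are part of Group 1's app use; no pre-prompt measurement of visits or calories is described. A prompt that works at once and steadily would therefore appear as a difference in level between groups, with parallel trajectories. That term has no within-person baseline to protect it and is exposed to whatever mix of cities and sexes each arm receives.

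**Working it through.** The plan gives no power calculation, effect size, SD, visit rate or city variance, so there is no planned figure to reproduce. Three checks follow.

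**1. How often would city mix differ by chance?**

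Inputs: three cities and three arms (C.3.a, C.3.b). Assumed: simple 1:1:1 allocation, equal city shares, and a total of 150 or 450. The measure is the largest difference in any city's share between two given arms, over 20,000 simulated allocations.

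| Total | ≥10 points | ≥15 points |
|---|---|---|
| 150 | 55% | about 26% |
| 450 | 16% | 1.7% |

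With 150, the largest and smallest arms differ by 10 or more participants in about 60% of simulated trials.

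As an illustration, suppose that a city with k times the visit rate of the others holds 26% of one arm and 41% of the other. With no treatment effect, the ratio of mean rates in that single trial is (1 + 0.41(k−1)) / (1 + 0.26(k−1)):
- k = 1.5: 1.205 / 1.130 = 1.07
- k = 2: 1.41 / 1.26 = 1.12

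These are displacements of the level ratio in a trial that happens to be imbalanced. They average out over randomisations. The values of k are assumed.

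**2. Which term can baseline covariates help?**

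For calories the model is Y = β0 + β1·Time + β2·Group + β3·Time×Group + error. A time-constant city or sex effect adds the same amount to all of a person's records, so with complete data it drops out of the slope. In the log-linear visit model it multiplies all of a person's rates by the same factor, which again leaves the slope on the log scale unchanged.

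Simulated GEE fits (exchangeable correlation, 50 per arm, four time points, 300 runs per scenario) compared the variance of β3 with and without city and sex main effects:
- Complete data: ratio 1.000 (linear at 5% and 10% explained variance; Poisson at 5%).
- 40% of records missing at random, linear: ratio 0.98 to 1.00.

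A constant treatment effect, by the same algebra, falls in β2 and leaves β3 at zero. In 200 simulated Poisson trials (50 per arm, four periods, constant 20% reduction, city rates 1 : 1.25 : 1.75, all assumed), the time-by-group term was rejected in 6.5%. The SE of the level comparison was 0.108 without city and 0.098 with it, a cut of 1 − 0.098/0.108 = 9%.

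**3. How much could the level comparison gain?**

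If the covariates explain a share s of person-level variance, the SE is multiplied by √(1−s), and the gain is worth 1/(1−s) − 1 in extra participants. Power is for a comparison of mean levels that starts at 80%, two-sided 5% (assumed).

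| s | SE cut | Equivalent extra participants | Power |
|---|---|---|---|
| 5% | 1 − √0.95 = 2.5% | 1/0.95 − 1 = 5% | 82.0% |
| 10% | 1 − √0.90 = 5.1% | 1/0.90 − 1 = 11% | 84.0% |
| 20% | 1 − √0.80 = 10.6% | 1/0.80 − 1 = 25% | 87.9% |

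**The case against.** The strongest objection is that C.3.e frames the models as comparing trajectories, so the time-by-group term is the planned contrast and the proposed covariates leave it almost untouched. This stands. A reader might infer that both planned comparisons lose precision throughout, or that a city imbalance shifts the trajectory result by the 1.07 or 1.12 shown above. The documents do not support either: those figures belong to the level comparison alone. The objection does not dispose of the point, because Aim 3 is worded in terms of levels and no pre-prompt baseline is described.

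Other limits also stand:
- A reader might infer that allocation is unblocked. The text is silent on blocks and strata; simple randomisation is an assumption here.
- A reader might infer about 50 per arm. The wording also allows 450 in total, where a 10-point imbalance is much less common.
- Virtual recruitment may have loosened the city structure, and sex is not a recruitment factor.
- The remark about neighborhood and school concerns recognition accuracy, calls these factors only potentially correlated, and belongs to a week that the amendment does not repeat. It is weak evidence that visits or calories differ by city.
- Chance imbalance does not bias a randomised comparison, and a valid standard error already allows for it.
- This is a pilot whose headed primary outcome is feasibility, and its secondary models have an open covariate list. That list names neither city, sex nor age, and it does not apply to the main models.

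**Conclusion.** The point holds as a minor matter of efficiency and reporting. The allocation method is not specified beyond random assignment at enrolment, and the main models omit baseline factors that should be readily available. The avoidable loss is confined essentially to the group main effect. There, adjustment would cut the SE by about 2.5–11% if city and sex explain 5–20% of person-level variance. That range is assumed; at 5% or less, the gain is about 2 points of power or fewer from an 80% start. The frequency of a 10-point city imbalance between two arms is about 55% or 16%, depending on whether the total is 150 or 450, and both figures assume simple 1:1:1 allocation. Any added benefit from age is also assumed. Nothing here shows bias or invalidates the planned analysis.

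**What to change.** 1. In C.3.b, state the allocation ratio and assign from a list prepared in advance, in permuted blocks of varying size. Stratify by city if city-based recruitment remains. Blocking also limits unequal arm sizes and drift between arms over calendar time during rolling enrolment.
2. In C.3.a, state whether city targets survive the move to virtual recruitment, and whether the total is 150 or 450.
3. In C.3.e, add city, sex and age at enrolment as fixed effects to both main GEE models. Report the adjusted group (level) effect alongside the time-by-group term. Fix the coding of time in advance, for example centred at mid-period, so that the group coefficient refers to a defined level.

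The cost is a prepared list for the technology team and a few model terms. Little or no new data should be needed: age and sex are required for the BMI-percentile criterion, and city is known if recruitment is by city. The technology team would still hold the allocation, so the blinding of the research assistant described in C.3.b is unaffected.

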Aim 2: To develop a message library adapted from the previously tested MPOWERed Messages library that can be tailored to students' food preferences, the menu options from their school and fast food venues, and incorporate cultural tailoring with input from the target population. [For this amendment we will utilize additional focus groups and an Adolescent Advisory board to provide additional input regarding the tailored messages and app design]

Aim 3: To explore, in a 1-month pilot, the acceptability, feasibility and use of the intervention developed in Aims 1 and 2, via usage data collected by the application plus semi-structured interviews with participants and with school personnel who might speak to any disruption to school functioning encountered during the pilot. [For this amendment we will pilot test the enhanced app to assess whether its use, over 6 months, is associated with fewer calories purchased from FFR and fewer visits to FFR.

We have shortened our study period time frame from 6 months to 1 month due to the COVID-19 pandemic.

This study will provide pilot data to inform our planned R01 proposal to test the impact of the intervention on behavior. We expect to develop LIITA³H as a marketable intervention, attractive to institutions interested in cost-effective means of improving health and impacting point of purchase choices. As a mHealth intervention, it can easily be scaled to include numerous participants. Further, the methodology may be adapted to address other conditions, offering the potential to reduce a wide range of health disparities.

RESEARCH STRATEGY

A. SIGNIFICANCE

African American (AA) adolescents have a disproportionately high prevalence of obesity, putting them at risk for a myriad of illnesses in their youth and for incurring a greater burden of morbidity and premature mortality than their Caucasian peers.

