C.1.a. Registration and Detection of Eating Venues with Intent to Eat. Detecting when students are in an eating venue with the intent to eat will use our personalized location information system (pLIS). A traditional Geographic Information System (GIS) assigns geographically referenced parameters to data types. For many cities a description of every street, business, bus stop, school and even smaller details are available. However, ‘full up’ GIS is too burdensome and expensive for individually targeted interventions and aren’t needed. Behaviors and environments experienced by a single person have interactions with a limited number of locations. This provides the opportunity to develop a GIS behavioral dataset for each individual, such as our pLIS. The system will dynamically integrate objective and context data into “just enough” mapping.

The personalized location information system (pLIS) will run on a student’s mobile phone to determine when they are in an eating location with the intent to eat. We will enhance and test functions to perform the following:

1. Rapidly determine location indoors and outdoors, using a "fused provider" service that combines cellular tower signal triangulation (E911) with satellite augmented GPS and local RF (e.g., WiFi) signals. will use the Google Location Application Programming Interface (<http://developer.android.com/google/play-services/location.html>).
2. Enable each student to mark a unique set of eating locations by the ActiPal and PiLR Healthware EMA tools (Figure 2).
3. Recognize presence in an eating venue with an “intent to eat” by:
 - a. Creating customizable recognition boundaries around each marked location, called “Geofencing”.
 - b. Assigning a “dwell time” of duration within the eating location boundary that can be modified by the participant and dietitian.
 - c. Assigning “meal times” for each participant that can be modified by students.
 - d. Using the EMA tools to ask students whether they intend to eat in a training period prior to delivery of tailored texts.

[For this amendment newly available databases and technology that make it feasible to automatically identify when users are in FFR, will be used to create an enhance location identification (ELI) system.

[figure not shown]

Figure 2. Location Registration Screen.

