Intervention Group 1 – Participants will be asked to keep the app running on their phone. They will receive a ping when the app identifies that they are in a fast food restaurant followed by a point of purchase prompt, tailored to their preferences and the options available at that location. If they are in a venue without a menu, general healthy suggestions will be provided (such as “consider choosing smaller portions” or “does this venue sell fruit?”). If the app does not ping when they enter a restaurant, they will be asked to register that location by tapping the ‘register location’ button on the app and entering the restaurant name. For detection errors, the appropriate stored venue criteria (location, geo-fence, time of day or dwell time) may be adjusted to improve detection. Users will also be asked to take a picture of any items they buy and to annotate it with information that would help to determine the nutrients in the food. Annotations may be audio, text, or made from a selection of descriptive buttons (e.g., to indicate small, medium or large sizes).

Control Group 2 – Participants in Control Group 2 will receive similar instructions to those given to group 1, but without receiving point of purchase prompts.

Control Group 3 – The Location Only Control Group 3 will only get information about location detection, and asked to register FFR if the app does not indicate with a ping that they have entered one. Their instructions will not discuss photo documentation of food or prompts as these features will not be active on their app.

During the study period, the participants will be contacted once per month by a research team member. Monthly calls will be added to help gather feedback from participants about the app. Study participants will be contacted by phone on three separate occasions, at times when the participants are not in school (e.g. after 4pm on weekdays or a weekend). If, for any reason, a research team member is unable to reach a study participant after three attempts, we will connect with the parent and/or research liaison (e.g. a staff member at the school or community organization we are working with) for assistance.

C.3.d Post Intervention Assessment

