Semi-Structured Interviews. At the completion of the 6-month trial (or sooner if they appear to have dropped out), adolescents will be interviewed to obtain detailed feedback about PiLR, the subject interface, methods of prompting, EMA surveys, entering data, submitting photos and rating foods. Location data will be used to inform the questions in the interview. For example, participants who, based on the GPS, have not visited FFR will be asked to share reasons for this change. Those who, based on the GPS, continue to visit FFR, will be asked about the choices made, and what if anything would be most helpful to them when they are making the choice regarding what to

purchase. They will also be asked about the user interface, cultural tailoring, and the SNAP component. Interviews will be transcribed and coded by 2 researchers separately.

For the semi-structured interviews at the end of the study period, study participants will be contacted by phone on three separate occasions, at times when the participants are not in school (e.g. after 4pm on weekdays or a weekend). If, for any reason, a research team member is unable to reach a study participant after three attempts, we will connect with the parent and/or research liaison (e.g. a staff member at the school or community organization we are working with) for assistance.

We have shortened our study period time frame from 6 months to 1 month due to the COVID-19 pandemic.

Quantitative Survey. *Acceptability Measure:* A questionnaire will assess acceptability of the format (What was their experience, did they like it?; How would you rate the overall experience?), and feasibility (How easy was it to use the hardware and respond to prompts?). Acceptability and feasibility mean scores of 3.5 or greater, rated on a scale of 1 (poor) to 5 (excellent), are deemed acceptable.

Assessment of Usage. *Electronic Usage Measures:* During the pilot, the PiLR will automatically record (1) the time students spent using the system, (2) the frequency of triggering events, (3) compliance with prompts, (4) and whether subjects felt the system was responsive. It will automatically record number of visits to the FFR. It will also collect usage data in regard to things like frequency of submitting pictures and whether they include annotations.

C.3.e. Analyses

Primary Outcome – Feasibility of the technological components

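### Fast food visits are counted by detection criteria that may be adjusted during follow-up, and the plan does not secure equal adjustment in all three arms

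*Combined protocol and SAP*

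**What the plan says.** Aim 3, as amended, asks whether use of the enhanced app "is associated with fewer calories purchased from FFR and fewer visits to FFR" (FFR: fast food restaurants). Follow-up has since been cut from 6 months to 1. On where the count comes from, section C.3.d says: "It will automatically record number of visits to the FFR". Section C.3.e says: "Frequency of visits will be obtained directly from the app". No other source is described. Section C.3.e compares visit trajectories between the three groups with a GEE Poisson model in time, group and their interaction.

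In section C.3.c, the paragraph on Intervention Group 1 allows detection settings to change in use: "For detection errors, the appropriate stored venue criteria (location, geo-fence, time of day or dwell time) may be adjusted to improve detection". The same paragraph asks participants to register a restaurant when the app fails to ping. For the second arm the plan says only: "Participants in Control Group 2 will receive similar instructions to those given to group 1, but without receiving point of purchase prompts". Group 3 participants are "asked to register FFR if the app does not indicate with a ping that they have entered one"; their paragraph does not mention adjusting criteria.

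Before the amendment, detection errors were to be corrected in week 2, ahead of message delivery. Section C.3.c now states "For this amendment weeks 1 to 3 will not be repeated". Detection accuracy appears in section C.3.e as a feasibility percentage, with no link to the visit model. The plan does not freeze the criteria, log their versions, re-score visits under one rule, or say whether a self-registered visit counts.

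**The concern.** The same settings do two jobs: they decide when a participant is pinged, and they decide what is counted as a visit. Improving them helps the first job and changes the measuring instrument for the second. With no calibration period, that change falls inside the randomised month.

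Two consequences follow, and they are not equally certain. A net change in detection appears as a change in visits over time within a group, whatever participants do. The comparison between groups is materially affected only if detection changes by different amounts in different arms. Randomisation balances participants at assignment, but it does not keep an instrument the same across arms afterwards. At stake is whether the visit result, which is meant to inform the planned larger trial, reflects behaviour or detection.

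**Working it through.** The documents give no detection sensitivity, false-detection rate, variance, significance level, target effect or sample-size calculation for visits, so there is no stated figure to reproduce. What can be checked is how a change in detection passes through the planned model.

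Inputs from the documents:
- True visits: 3 per week, the eligibility minimum in C.3.a, held constant.
- Follow-up: 1 month, taken as four weekly counts.
- Model: GEE Poisson with log link and a time-by-group term (C.3.e).
- Group size: C.3.a can be read as 150 in all or 150 in each of 3 cities. With equal allocation (not stated) that is 150/3 = 50 or 450/3 = 150 per group.

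Assumptions: sensitivity *s*; false detections *f* per week; between-participant gamma variance 0.5; two-sided 0.05.

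Formulas: observed weekly count = *s* × true visits + *f*. Trend RR = week-4 count / week-1 count. Interaction RR = Group 1 trend RR / control trend RR.

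**Step 1: the same drift in every arm.** Let *s* rise from 0.70 to 0.90 with *f* = 0.
- No true effect: each arm shows (0.90 × 3)/(0.70 × 3) = 2.7/2.1 = 1.286, a false rise. The interaction is 1.286/1.286 = 1.000.
- True RR of 0.80 in Group 1: (2.7 × 0.80)/2.1 = 2.16/2.1 = 1.029, and 1.029/1.286 = 0.80. The effect is recovered.
- If *f* also falls from 1.0 to 0.2 in both arms: Group 1 is (2.16 + 0.2)/(2.1 + 1.0) = 0.761, control is (2.7 + 0.2)/(2.1 + 1.0) = 0.935, and the ratio is 0.81. The additive part leaves a small residue.

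**Step 2: drift in Group 1 only, no true effect.** The control trend is 1, so the interaction equals the Group 1 trend.

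| Change in Group 1 | Calculation | False interaction RR |
|---|---|---|
| *s* 0.80 to 0.85, *f* = 0 | 2.55/2.40 | 1.06 |
| *s* 0.70 to 0.80, *f* = 0 | 2.40/2.10 | 1.14 |
| *s* 0.70 to 0.90, *f* = 0 | 2.70/2.10 | 1.29 |
| *f* 0.5 to 0.2, *s* = 0.90 | 2.9/3.2 | 0.91 |
| *f* 1.0 to 0.2, *s* = 0.90 | 2.9/3.7 | 0.78 |

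**Step 3: drift on top of a real benefit.** With a true RR of 0.80 and *s* rising from 0.70 to 0.90 in Group 1 only, the model sees 0.80 × 0.90/0.70 = 1.03. The benefit disappears.

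**Step 4: how often the planned test would react.** Each setting was simulated 400 times: Group 1 against one control, linear change over the four weeks, exchangeable correlation, robust standard errors, no true effect. Simulation error near 5% is √(0.05 × 0.95/400) = 1.1 percentage points.

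| Setting | Interaction rejected, 50 per group | Interaction rejected, 150 per group |
|---|---|---|
| No drift | 6% | 6% |
| *s* 0.70 to 0.90 in both arms | 5% | 4% |
| *s* 0.70 to 0.80, Group 1 only | 9% | 31% |
| *s* 0.70 to 0.90, Group 1 only | 30% | 67% |
| *f* 1.0 to 0.2, Group 1 only | 40% | 84% |

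Under common drift (second row) the interaction test keeps its size, but the time trend in the control group is falsely declared in 56% of runs at 50 per group and 94% at 150.

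**The case against.** The strongest reply is that the planned comparison is between groups. A reader might infer that any re-tuning biases the treatment contrast. It does not: Step 1 shows that equal proportional drift cancels. That part of the reply stands.

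A reader might also infer that Group 1 is tuned and Group 3 is not. The documents do not say so. Group 2 differs from Group 1 only in the prompts, so the natural reading is that tuning applies there too, and the contrast that isolates the prompts may be well protected. Group 3 also receives pings and registers missed restaurants, and location detection is not listed among its inactive features. Silence on adjusting stored criteria is not exclusion. Yet the plan does not state equality either. Section C.3.b tells participants their assignment and describes only the data-collecting research assistant as blinded, and C.3.c does not say who makes the adjustments.

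It is tempting to suppose that the prompted arm has more reason to report errors. Nothing in the text supports this; Group 3's main task is location detection, so it could report as much or more.

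Section C.1.a describes a dwell time "that can be modified by the participant and dietitian", but that is the pre-amendment location system. The amended system identifies restaurants automatically from databases and may need less tuning. C.3.c does keep dwell time among the adjustable criteria. Nor was calibration ever wholly confined to week 2, since students could add venues throughout. Finally, adjustment is permitted rather than required, and this is a pilot. These points limit the likely size of the problem. They do not supply a rule that keeps the count comparable across weeks and arms.

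**Conclusion.** The point holds with a limited reach. As written, the visit outcome can mix changes in detection with changes in behaviour. Within-group trends are exposed to any net change in detection. The time-by-group contrast is materially exposed only to changes that differ by arm, which the plan neither establishes nor prevents.

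Under the assumptions above, arm-specific changes give false interaction RRs from 1.06 to 1.29 when sensitivity rises in Group 1, and from 0.91 to 0.78 when its false detections fall. The bias can therefore hide a benefit or create one. The true size is unknown, because the documents give no detection rates and do not say how much adjustment will occur. A reader might want to set these ratios against the effect that the trial hopes to see; no target effect is stated, so that comparison cannot be made. The rejection percentages depend further on the unresolved group size and the assumed variance.

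**What to change.** Separate the outcome count from the live system, so that adjustments during follow-up drive pings and prompts only.

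- If location and time records are stored, compute visits at database lock with one fixed rule (one restaurant database version, geofence radius, dwell time and time-of-day window) for all participants, arms and weeks.
- If they are not stored, freeze the criteria that define the outcome at enrolment and log every later change.
- State that adjustment and registration procedures are identical in all three arms.
- Tabulate self-registered visits by arm and week, and use them only in a sensitivity analysis.

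Cost: the first option needs analysis-plan wording and one re-scoring run. It depends on records being retained: section C.3.d refers to location data, but the documents never say that a continuous track is kept. The fallback is a real change to how the app is operated. Either way, the fixed rule may miss some visits that a tuned rule would catch. Live prompting is unaffected.
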